**Non-PK Study Subjects:**

Those subjects not participating in the PK subset will check into the clinical investigative site in the morning of Day 1 and will remain at the clinical investigative site until after the first dose on Day 1 and all safety assessments have been completed.

With the exception of the first dose of study drug administered at the clinical investigative site on Day 1, subjects will administer study drug at home for all remaining doses through Day 28.

PK Subset Safety Subjects:

Those subjects participating in the PK subset will follow the same general schedule with the addition of several overnight stays. Specifically, the PK subset will consist of a screening period (Day -28 to Day -2), 3 check-in and in house periods (Day -1 to Day 2; Day 13 to Day 14; and Day 27 to Day 31), a dosing complete/ET visit (Day 29), and 2 follow-up telephone calls (Day 42 [+2 days] and Day 58 [+2 days]).

Subjects in the PK subset will check into the clinical investigative site on Day -1, Day 13, and Day 27 and be discharged from the clinical investigative site on Day 2, Day 14, and Day 31. Subjects will check into the clinical investigative site early enough to eat the required meal and then be administered the final dose for that day on Day 13 and Day 27.

When the study drug is not administered at the clinical investigative site, subjects will administer study drug at home.

Serial blood samples for PK analysis of TPOXX will be collected before the first dose (0 hour) on Days 1, 14, and 28 and up to 24 hours after study drug administration on Day 1 and up to 72 hours after study drug administration on Day 28.

## **4. STUDY POPULATION**

A total of at least 445 adult male and female subjects will be enrolled at approximately 12 clinical investigative sites in the United States.

### **4.1 INCLUSION CRITERIA**

Each subject must meet all of the following criteria to be enrolled in this study:

1. Subject is male or female between 18 and 80 years of age, inclusive.
2. Subject is available for clinical follow-up for the duration of the study.
3. Women of childbearing potential have a negative  $\beta$ -human chorionic gonadotropin pregnancy test (serum) at the screening visit and a negative urine pregnancy test on Day 1 or Day -1 (PK subset) before receipt of study drug, and meet one of the following criteria:
  - a. Subject or their partner has undergone surgical sterilization.

- b. Male sexual partner who had undergone a vasectomy at least 3 months before screening
- c. Subject is postmenopausal, defined as 12 consecutive months with no menses without an alternative medical cause and has a documented plasma follicle-stimulating hormone level >40 IU/mL.
- d. Subject agrees to be abstinent (i.e., heterosexually inactive) for the duration of the study.
- e. Subject agrees to consistently use 1 of the following methods of contraception from the beginning of screening (which they had been consistently using for at least 30 days before the first dose of study drug) through 30 days after the last dose of study drug:
  - i. Condoms, male or female, with a spermicide

**NOTE:** For male subjects, condoms must be used for 90 days after the last dose of study drug. Male and female condoms should not be used together, as this can reduce their effectiveness.

- ii. Diaphragm or cervical cap with spermicide
- iii. Intrauterine device with spermicide
- iv. Oral contraceptives or other hormonal methods

**NOTE:** Another nonhormonal method of contraception must be used in conjunction with oral contraceptives.

- 4. Male subjects must agree to not donate sperm from the first dose of study drug through 90 days after the last dose of study drug.
- 5. Subject is considered by the investigator to be in good general health as determined by medical history (no hospitalizations for chronic medical conditions in the previous 2 years), clinical laboratory test results, vital sign measurements, 12-lead ECG results, and physical examination findings at screening.
- 6. Subject agrees not to use nicotine products, including electronic vapor cigarettes, nicotine patches, or nicotine gum, for at least 30 days before the Day 1 randomization visit through completion of the Day 29 dosing complete/ET visit.

7. Subject agrees to comply with the study dietary requirements throughout the study drug dosing period.
8. Subject agrees not to consume caffeine- or xanthine-containing products during all study visits, including overnight stays (PK subset); sodas, coffee, and tea designated as caffeine-free or noncaffeinated may be consumed on study days; caffeine may be consumed while at home and between study visits.
9. Subject agrees to comply with all protocol requirements.
10. Subject has adequate venous access if participating in the PK subset.
11. Subject is able and willing to provide written informed consent.

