**STUDY POPULATION:**

**Inclusion Criteria:**

Each subject must meet all of the following criteria to be enrolled in this study:

1. Subject is male or female between 18 and 80 years of age, inclusive.
2. Subject is available for clinical follow-up for the duration of the study.
3. Women of childbearing potential have a negative  $\beta$ -human chorionic gonadotropin pregnancy test (serum) at the screening visit and a negative urine pregnancy test on Day 1 or Day -1 (PK subset) before receipt of study drug, and meet one of the following criteria:

- a. Subject or their partner has undergone surgical sterilization.
- b. Male sexual partner who has undergone a vasectomy at least 3 months before screening.
- c. Subject is postmenopausal, defined as 12 consecutive months with no menses without an alternative medical cause and has a documented plasma follicle-stimulating hormone level >40 IU/mL.
- d. Subject agrees to be abstinent (i.e., heterosexually inactive) for the duration of the study.
- e. Subject agrees to consistently use 1 of the following methods of contraception from the beginning of screening (which they had been consistently using for at least 30 days before the first dose of study drug) through 30 days after the last dose of study drug:
  - i. Condoms, male or female, with a spermicide

**NOTE:** For male subjects, condoms must be used for 90 days after the last dose of study drug. Male and female condoms should not be used together, as this can reduce their effectiveness.

- ii. Diaphragm or cervical cap with spermicide
- iii. Intrauterine device with spermicide
- iv. Oral contraceptives or other hormonal methods

**NOTE:** Another nonhormonal method of contraception must be used in conjunction with oral contraceptives.

4. Male subjects must agree to not donate sperm from the first dose of study drug through 90 days after the last dose of study drug.
5. Subject is considered by the investigator to be in good general health as determined by medical history (no hospitalizations for chronic medical conditions in the previous 2 years), clinical laboratory test results, vital sign measurements, 12-lead ECG results, and physical examination findings at screening.
6. Subject agrees not to use nicotine products, including electronic vapor cigarettes, nicotine patches, or nicotine gum, for at least 30 days before the Day 1 randomization visit through completion of the Day 29 dosing complete/ET visit.

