## **1.4 POTENTIAL RISKS AND BENEFITS**

### **1.4.1 Potential Risks**

The effect of TPOXX on a fetus or nursing baby is not yet known; therefore, women of childbearing potential participating in this study will be required to agree to use an acceptable means of birth control from signing of the informed consent form (ICF) and continuing through 30 days after the last dose of study drug. For all women of childbearing potential, serum pregnancy testing will be performed and checked by the investigator to confirm a negative test result at the screening visit. For women of childbearing potential in the pharmacokinetic (PK) subset, a urine pregnancy test will be performed at check-in on Day -1 and must be confirmed as negative by the investigator prior to randomization and before receipt of the first dose of study drug on Day 1. Additional serum pregnancy testing will be performed on Days 7, 13, 21, and on Day 29 dosing complete/early termination (ET) visit. For women of childbearing potential not in the PK subset, a urine pregnancy test will be performed at check-in on Day 1 and must be verified as negative by the investigator prior to randomization and before receipt of the first dose of study drug. Additional serum pregnancy testing will be performed on Days 7, 14, 21, and on Day 29 dosing complete/ET visit. Women who are pregnant or breastfeeding or plan to become pregnant within 3 months after study drug administration will be excluded from the study; if a female subject becomes pregnant during study participation, study drug dosing will be discontinued, and the subject will be withdrawn from the study ([Section 6.2.1.8](#)).

As with all drugs, there is potential risk of an allergic reaction. At this time, there is no definitive information on the allergic activity of TPOXX. Headache and nausea have been the most common adverse events (AEs) in clinical studies completed to date. There may be other side effects of TPOXX that are not yet known. Full details can be found in the TPOXX full prescribing information.

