  - Aspartate aminotransferase >2 times above the upper laboratory reference range
  - Alkaline phosphatase >20% above the upper laboratory reference range
  - Hemoglobin A1c  $\geq$ 7.0%
  - Cholesterol  $\geq$ 300 mg/dL and low-density lipoprotein  $\geq$ 190 mg/dL

27. Subject has hypertension that is poorly controlled (repeat readings  $>140$  mm Hg systolic and/or  $>90$  mm Hg diastolic) or blood pressure considered to be clinically significant by the investigator. Blood pressure may be retested twice in the sitting position at 5-minute intervals.
28. Subject has a resting heart rate of  $<40$  beats per minute or  $>110$  beats per minute at screening.
29. Subject has an abnormal ECG at screening that is determined by the investigator to be clinically significant.
30. Male subject has a QT interval corrected using Fridericia's formula (QTcF)  $>450$  ms or female subject has a QTcF  $>470$  ms at screening or Day 1, or Day -1 (PK subset).
31. Subject has used any prescription antiviral drugs with the intention of coronavirus disease (COVID-19) treatment or prophylaxis, including those that are thought to be effective for prevention of COVID-19 but have or have not been licensed for this indication, within 1 month prior to study entry or during the study.
32. In the opinion of the investigator, the subject is not suitable for entry into the study.
33. Subject is a member or family member of the investigator or study site personnel.
34. Subject has previously participated in this clinical trial.

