#### **3.1.1 Inclusion Criteria**

As stated in Protocol Section 4.1.

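### Inclusion criterion 3a accepts a partner's surgical sterilisation with no minimum interval, so the 3-month vasectomy rule in 3b has no effect as written

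*Combined protocol and SAP*

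**What the plan says.** Criterion 3 in Protocol Section 4.1 applies to women of childbearing potential. It requires negative pregnancy tests, "and meet one of the following criteria", and then lists items a to e. Two of them concern sterilisation:

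- 3a: "Subject or their partner has undergone surgical sterilization". There is no interval and no exception for vasectomy.
- 3b: "Male sexual partner who had undergone a vasectomy at least 3 months before screening".

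The other routes are postmenopausal status (3c), abstinence (3d) and consistent use of a listed contraceptive method (3e). The Synopsis has the same list, with 3b worded "Male sexual partner who has undergone a vasectomy at least 3 months before screening".

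Four other places bear on the point:

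- Protocol Section 1.4.1 sets a general undertaking for these women, "use an acceptable means of birth control from signing of the informed consent form (ICF) and continuing through 30 days after the last dose", and does not say what counts as acceptable. It also states: "The effect of TPOXX on a fetus or nursing baby is not yet known".
- Protocol Section 6.2.1.8 requires counselling on the prevention of pregnancy.
- Exclusion criterion 32 allows refusal when "In the opinion of the investigator, the subject is not suitable for entry into the study".
- SAP Section 3.1.1 adds nothing: "As stated in Protocol Section 4.1".

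**The concern.** The sponsor wrote a separate item for vasectomy and gave it a 3-month interval. Because the items are alternatives, that interval binds only if no other item admits the same couple without it. Item 3a names the partner and sets no time limit, so it appears to admit the couples that 3b is meant to hold back.

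What is at stake is subject protection and consistent screening. A woman whose only qualifying route is her partner's very recent vasectomy could be enrolled in full compliance with the text and given a drug whose fetal effects the protocol describes as unknown. Different sites could also decide the same case differently, each with a defensible reading.

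**Working it through.** The plan states no figure on this point. The check is one of logic, with a short timing illustration.

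**Step 1: the list as written.** Let S = the subject is surgically sterilised, V = the partner has had a vasectomy, and m = months from vasectomy to screening. Assume that a vasectomy is surgical sterilisation of the partner.

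- 3a is met if S or V.
- 3b is met if V and m ≥ 3.
- Criterion 3 (contraception part) is met if 3a or 3b or 3c or 3d or 3e.

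Anyone with V and m ≥ 3 has V, so meeting 3b implies meeting 3a. The criterion therefore reduces to 3a or 3c or 3d or 3e, and 3b drops out.

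**Step 2: enumeration.** I crossed S (yes/no), V (yes/no), m (0.25, 1, 2, 2.9, 3, 6, 12 months) and 3c, 3d, 3e (each yes/no): 2 × 2 × 7 × 2 × 2 × 2 = 224 profiles.

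- Deleting 3b changes eligibility in 0 of 224.
- Making the 3-month rule govern vasectomy changes eligibility in 4 of 224: the woman is not sterilised, meets none of 3c to 3e, and her partner's vasectomy was 0.25, 1, 2 or 2.9 months before screening.

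These counts describe the logic of the list. They are not an estimate of how often the case occurs.

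**Step 3: does other text restore the interval?**

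| Text | What it does | Sets an interval? |
|---|---|---|
| Section 1.4.1 | Requires agreement to acceptable birth control | No; acceptable is undefined |
| Section 6.2.1.8 | Requires pregnancy-prevention counselling | No |
| Exclusion 32 | Allows the investigator to refuse a subject | No; discretionary |
| SAP 3.1.1 | Points back to Section 4.1 | No |

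No text defines surgical sterilisation, removes vasectomy from 3a, or says that 3b overrides 3a.

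**Step 4: what the interval would require.** Assume 3 months = 90 days (89 to 92 by calendar). Screening runs from Day -28 to Day -1 in Table 9-2 (to Day -2 in Section 3 and Table 9-1). By the SAP's study-day rule, Day -n is n days before the first dose.

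- Under 3b, the vasectomy is at least 90 + 1 = 91 to 90 + 28 = 118 days before the first dose, depending on the screening day (lower end 90 + 2 = 92 with Day -2).
- Under 3a, there is no minimum. Extreme case, vasectomy 1 day before screening: its age is 1 + 1 = 2 to 1 + 28 = 29 days at the first dose; adding 27, it is 29 to 56 days at Day 28; adding 57 instead, it is 59 to 86 days at Day 58. In that case all dosing and the 30 days after it fall inside 3 months of the vasectomy.

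**The case against.** The strongest reply is that this is only a drafting overlap. The protocol has a dedicated vasectomy item, and on an ordinary reading the specific item governs the general one. The enumeration cannot settle that, because it assumes that vasectomy falls within 3a. This is fair as to intent: 3b was very probably meant to control, and many sites would read it so. But the text makes the items alternatives and 3a names the partner. A site that admitted such a woman under 3a would have followed the list exactly, and 3b could not be cited against it.

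The second reply is that other controls exist. Counselling in Section 6.2.1.8 is mandatory and preventive. Section 1.4.1 separately requires agreement to acceptable birth control. Exclusion 1 removes women planning pregnancy within 3 months after the last dose, and dosing stops if pregnancy occurs. These stand, and they lower the risk. None replaces the interval.

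The third reply is that day counts do not measure harm. That is also right. The documents give neither a number of such couples nor a pregnancy probability. In addition, 3b counts from screening, so some vasectomies that fail it are already old enough by the first dose. For example, one performed 80 days before a Day -28 screening visit is 80 + 28 = 108 days old at the first dose, beyond 90.

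**Conclusion.** The point holds as a minor subject-protection correction. On the ordinary meaning of surgical sterilisation, the 3-month interval in 3b has no effect as written, in Section 4.1 and in the Synopsis alike. The conclusion rests on that meaning, which the protocol neither states nor excludes.

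A reader might go further and infer that women will in practice be enrolled without protection against pregnancy, or that only the investigator's discretion stands in the way. The documents do not support that: the intent of 3b is plain, counselling is mandatory, and agreement to birth control is required. Nor do they support any inference about the trial's results. The number of women affected is unknown and probably small, and no endpoint, sample size or planned analysis changes.

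**What to change.** In Section 4.1 and the Synopsis, reword 3a to: *Subject has undergone surgical sterilization, or their partner has undergone surgical sterilization other than vasectomy.* Item 3b then alone governs vasectomy, and a partner sterilised in another way remains acceptable.

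The change is one sentence in two places, with no new procedure. It removes only women whose sole route is a partner's vasectomy less than 3 months before screening. They would have to qualify through abstinence (3d), through 3e, or by being screened later. Item 3e is not open to someone starting a method at screening: it needs at least 30 days of use before the first dose and screening lasts at most 28 days, so the method must already have been in use for 30 - 28 = 2 to 30 - 1 = 29 days before the screening visit. For a few couples that means a delay, which is the effect 3b was evidently meant to have.

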## **4.2 EXCLUSION CRITERIA**

Subjects meeting any of the following criteria will be excluded from the study:

1. Subject is a female who is pregnant or breastfeeding or planning to become pregnant within 3 months after the last dose of study drug.
2. Subject has a history of any clinically significant conditions including:
  - Asthma treated with oral systemic steroids within the past 6 months
  - Diabetes mellitus (type 1 or 2), with the exception of gestational diabetes
  - Thyroidectomy or thyroid disease that required medication within the past 12 months
  - Serious angioedema episodes within the previous 3 years or requiring medication in the previous 2 years
  - History of head trauma resulting in a diagnosis of traumatic brain injury other than concussion
  - Frequent episodes of headache
3. Subject has received any vaccination within 28 days prior to Day 1 or plans to receive a vaccination at any time during the treatment period or within 28 days after study Day 28.

4. Subject has received treatment in another clinical study of an investigational drug (or medical device) or investigational vaccine within 30 days or 5 half-lives (whichever is longer) before the first dose of study drug.
5. Subject has a history of relevant drug and/or food allergies (i.e., allergy to TPOXX or excipients, or any significant food allergy that could preclude a standard diet in the clinical investigative site).
6. Subject has any condition possibly affecting drug absorption (e.g., previous surgery on the gastrointestinal tract, including removal of parts of the stomach, bowel, liver, gallbladder, or pancreas, with the exception of appendectomy).
7. Subject has evidence or history of clinically significant allergic reaction(s) (excluding seasonal allergies); or has evidence or history of clinically significant disease, including hematological, endocrine, pulmonary, gastrointestinal, cardiovascular, hepatic, psychiatric, or neurological disease. Exceptions to these disease criteria (e.g., stable, mild joint disease unassociated with collagen vascular disease) may be made following discussions with the medical monitor.
8. Subject has a history of cardiac disease, symptomatic or asymptomatic arrhythmias, syncopal episodes, chest pain (that is diagnosed as cardiac related) or trouble breathing on exertion, or risk factors for torsades de pointes (e.g., heart failure, hypokalemia).
9. Subject has a family history of an immediate family member (father, mother, brother, or sister) who parents and/or siblings) who has had an onset of ischemic heart disease before the age of 50 years.
10. Subject is 20 years of age or older and has a  $\geq 30\%$  risk of developing a myocardial infarction or coronary death within the next 10 years using the National Cholesterol Education Program's Risk Assessment Tool: <https://www.mcw.edu/calculators/ldl-cholesterol-goal-level>.
11. Subject has a seizure disorder or history of seizures (does not include childhood febrile seizures) or a past history that increases seizure risks such as significant head injury that caused loss of consciousness or other changes in the subject's daily function, concussion, stroke, central nervous system infection or disease, or alcohol or drug abuse or family history of idiopathic seizures.
12. Subject has a history of a peptic ulcer or significant gastrointestinal bleeding.

13. Subject has a bleeding disorder diagnosed by a doctor (e.g., factor deficiency, coagulopathy, or platelet disorder requiring special precautions) or significant bruising or bleeding difficulties with blood draws.
14. Subject has a malignancy that is active or treated malignancy for which there is not reasonable assurance of sustained cure, or malignancy that is likely to recur during the period of the study (subject should be in complete remission for at least 5 years).
15. Subject has neutropenia or other blood dyscrasia determined to be clinically significant by the investigator.
16. Subject has used any of the following prohibited medications from within 7 days (or 5 half-lives, whichever is longer) before the first dose of study drug: antidiabetic medication; anticoagulants; anticonvulsants; substrates of the breast cancer resistance protein transporter including methotrexate, mitoxantrone, imatinib, irinotecan, lapatinib, rosuvastatin, sulfasalazine, and topotecan; substrates of cytochromes (CYP)2C8 including repaglinide, paclitaxel, montelukast, pioglitazone, rosiglitazone; and substrates of CYP2C19 including S-mephénytoin, clobazam, diazepam, rabeprazole, voriconazole, lansoprazole, and omeprazole. Medications not listed here that are known (or thought) to be CYP3A4 substrates may be allowed at the investigator's discretion, after consultation with the medical monitor, if administration poses little to no risk to the subject.
17. Subject has a history of drug or alcohol abuse or dependency within the last year before screening.
18. Subject has a current or recent (<30 days before screening) history of clinically significant bacterial, fungal, or mycobacterial infection.
19. Subject has a current clinically significant viral infection.
20. Subject has a known clinically significant chronic viral infection (e.g., human T cell lymphotropic virus I or II).
21. Subject demonstrates long-term use ( $\geq 14$  consecutive days) of glucocorticoids, including oral or parenteral prednisone or equivalent ( $>20$  mg total dose per day), or high-dose inhaled steroids ( $>800$  mcg/day of beclomethasone dipropionate or equivalent) within the preceding 1 month (low-dose [ $\leq 800$  mcg/day of beclomethasone dipropionate or equivalent] inhaled and topical steroids are allowed).

22. Subject has donated >450 mL blood or blood components within 30 days before the first dose of study drug. The investigator should instruct subjects who participate in this study to not donate blood or blood components for 4 weeks after the completion of the study.
23. Subject reports participation in strenuous activity or contact sports within 24 hours before the first dose of study drug.
24. Subject has known hepatitis B or C infection or positive test for hepatitis B surface antigen, hepatitis C virus antibody, or human immunodeficiency virus type 1 or 2 antibodies at screening.
25. Subject has a positive test result for amphetamines (including methamphetamines and ecstasy/methylenedioxymethamphetamine), barbiturates, benzodiazepines, cannabinoids (including tetrahydrocannabinol), cocaine metabolites, opiates (including heroin, codeine, and oxycodone), cotinine, or alcohol at screening or check-in.
26. Subject has any of the following laboratory test results within 28 days before the first dose of study drug:
  - Estimated serum creatinine clearance (Cockcroft-Gault) <70 mL/min
  - Creatinine in males >1.7 mg/dL and in females >1.4 mg/dL (1.3 times the upper laboratory reference range)
  - Hemoglobin  $\leq$ 10% of the lower laboratory reference range
  - White blood cell counts considered to be clinically significant by the investigator
  - Absolute neutrophil count <1000 cells/mm^3
  - Platelets not within  $\pm$ 10% of laboratory reference range
  - Alanine aminotransferase >2 times above the upper laboratory reference range
  - Aspartate aminotransferase >2 times above the upper laboratory reference range
  - Alkaline phosphatase >20% above the upper laboratory reference range
  - Hemoglobin A1c  $\geq$ 7.0%
  - Cholesterol  $\geq$ 300 mg/dL and low-density lipoprotein  $\geq$ 190 mg/dL

27. Subject has hypertension that is poorly controlled (repeat readings  $>140$  mm Hg systolic and/or  $>90$  mm Hg diastolic) or blood pressure considered to be clinically significant by the investigator. Blood pressure may be retested twice in the sitting position at 5-minute intervals.
28. Subject has a resting heart rate of  $<40$  beats per minute or  $>110$  beats per minute at screening.
29. Subject has an abnormal ECG at screening that is determined by the investigator to be clinically significant.
30. Male subject has a QT interval corrected using Fridericia's formula (QTcF)  $>450$  ms or female subject has a QTcF  $>470$  ms at screening or Day 1, or Day -1 (PK subset).
31. Subject has used any prescription antiviral drugs with the intention of coronavirus disease (COVID-19) treatment or prophylaxis, including those that are thought to be effective for prevention of COVID-19 but have or have not been licensed for this indication, within 1 month prior to study entry or during the study.
32. In the opinion of the investigator, the subject is not suitable for entry into the study.
33. Subject is a member or family member of the investigator or study site personnel.
34. Subject has previously participated in this clinical trial.

